8.5.2 Method of Detecting AEs, SAEs, and Other Reportable Safety Events

Care will be taken not to introduce bias when detecting AEs and/or SAEs and other reportable safety events. Open-ended and nonleading verbal questioning of the participant is the preferred method to inquire about AE occurrence.

8.5.3 Follow-up of AE, SAE, and Other Reportable Safety Event Information

After the initial AE/SAE report, the investigator is required to proactively follow each participant at subsequent visits/contacts. All AEs, SAEs, and other reportable safety events, including cancer and overdose will be followed until resolution, stabilization, until the event is otherwise explained, or the participant is lost to follow-up (as defined in Section 7.3). In

75

PROTOCOL/AMENDMENT NO.: 064-03

addition, the investigator will make every attempt to follow all nonserious AEs that occur in randomized participants for outcome. Further information on follow-up procedures is given in Appendix 3.

8.5.4 **Regulatory Reporting Requirements for SAE**

Prompt notification (within 24 hours) by the investigator to the Sponsor of SAE is essential so that legal obligations and ethical responsibilities toward the safety of participants and the safety of a study intervention under clinical investigation are met.

The Sponsor has a legal responsibility to notify both the local regulatory authority and other regulatory agencies about the safety of a study intervention under clinical investigation. The Sponsor will comply with country-specific regulatory requirements and global laws and regulations relating to safety reporting to regulatory authorities, IRB/IECs, and investigators.

Investigator safety reports must be prepared for SUSARs according to local regulatory requirements and Sponsor policy and forwarded to investigators as necessary.

An investigator who receives an investigator safety report describing an SAE or other specific safety information (eg, summary or listing of SAEs) from the Sponsor will file it along with the IB and will notify the IRB/IEC, if appropriate according to local requirements.

Note: To meet EU CTR requirements, the Sponsor will report SUSARs to the Eudravigilance database via E2B(R3) electronic ICSR form in compliance with CTR 536/2014.

8.5.5 **Pregnancy and Exposure During Breastfeeding**

Information in this section is not applicable since participants are males and partner pregnancy/lactation information are not applicable.

8.5.6 Disease-related Events and/or Disease-related Outcomes Not Qualifying as **AEs or SAEs**

None.

8.5.7 **Events of Clinical Interest**

None.

8.6 **Treatment of Overdose**

In this study, an overdose is defined as a participant receiving >1 dose of study vaccine in a 24-hour period or more than the number of doses of study vaccine specified in the protocol throughout the study.

Sponsor does not recommend specific treatment for an overdose.

Decisions regarding dose interruptions or modifications will be made by the investigator in consultation with the Sponsor Clinical Director based on the clinical evaluation of the participant.

8.7 Pharmacokinetics

PK parameters will not be evaluated in this study.

8.8 Pharmacodynamics

Pharmacodynamic parameters will not be evaluated in this study.

8.9 Biomarkers

Biomarkers are not evaluated in this study.

8.10 Future Biomedical Research Sample Collection

If the participant provides documented informed consent for FBR, the following specimens will be obtained as part of FBR:

DNA for future research

8.11 Health Economics Medical Resource Utilization and Health Economics

Health Economics OR Medical Resource Utilization and Health Economics are not evaluated in this study.

8.12 Visit Requirements

Visit requirements are outlined in Section 1.3. Specific procedure-related details are provided in Section 8.

8.12.1 Visit Requirements in Base Study

8.12.1.1 Screening Visit

The screening visit or the last screening visit (for re-screening) should be on the same day of randomization and the first dose of vaccination. Potential participants will be evaluated to determine that they fulfill the entry requirements as set forth in Section 5. Screening procedures may be repeated after consultation with the Sponsor.

If possible, all Day 1 visit procedures should be performed on the day of consent. If date of Day 1 visit (and all procedures) is later than consent date, the interval between the date of consent and the date of the Day 1 visit should be no more than 14 days. If the interval is 15 days or longer, then the participant must be reconsented.

8.12.1.2 Prerequisites for Vaccination Visit (Day 1, Month 2, and Month 6)

This section summarizes prerequisites for vaccination visits. See the inclusion/exclusion criteria for specific restrictions on Day 1 (see Section 5.1 and Section 5.2). At Month 2 and Month 6 study vaccination visits, study personnel should verify by questioning the participant and/or by examination that:

- 1. The participant has not had a fever (oral temperature ≥37.5°C) within the 24-hour period prior to the vaccination visit.
- 2. The participant has not received any systemic (oral or parenteral) corticosteroids in 14 days prior to the Month 2 and Month 6 study vaccination visits.
- 3. The participant has not received a non-study inactivated or recombinant vaccine within 14 days prior to any study vaccination visit or a non-study live vaccine within 28 days prior to any study vaccination visit.

If the participant does not meet the requirements listed above, the study visit (including specimen collection and study vaccination) should be re-scheduled.

8.12.1.3 Prerequisites for Anogenital Sample Collection Visits

See the inclusion/exclusion criteria for specific restrictions on Day 1 (see Section 5.1 and Section 5.2). For visits that include collection of study specimens, the site study personnel should verify by questioning the participant that he had not engaged in sexual activity within 48 hours nor shaved their genital region and/or applied any post-shave lotion or lubricants within 24 hours prior to any visit that includes collection of swabs, and/or biopsies specimens. See section 8.1.14 for details regarding documentation of sexual activity. If the participant does not meet the requirements listed above, the study visit should be rescheduled.

8.12.1.4 Early Termination Procedures

Once at least 17 primary efficacy endpoint cases and at least 17 secondary efficacy endpoint cases have been observed, initial database lock and unblinding will be performed and notified to the study sites. Following notification, participants remaining in the study (ie, who have not yet completed a Final Visit) will proceed to a Final Visit in the base study promptly. Under that scenario, participants who have not yet completed a Final Visit will complete the specified procedures in Final Visit in this Schedule of Activities.

Participants who have not yet completed Month 36 should schedule a Final Visit with collection of serum sample within the specific day ranges from Day 913 to Day 1277 (within the acceptable ranges for collection of serum sample, see Section 9.5.2), if possible. At the Final Visit, serum sample should not be collected from the participants who have already completed Month 36 or outside of the day ranges from Day 913 to Day 1277.

If the Sponsor elects to terminate earlier under this scenario, the limited procedures shown in the SoA (Section 1.3) will be conducted at the final visit as follows; update medical history,

review prior/concomitant medication and non-study vaccination review, monitor AEs, and blood sample collection for serum for anti-HPV (only for the participants who have not yet completed Month 36). Refer to Section 8.1.4, 8.1.6, 8.3.1 and 8.5, respectively, for the details of each procedure.

8.12.2 Visit Requirements in Extension Study

8.12.2.1 Prerequisites for Vaccination Visit (Extension Visit 1, Extension Visit 2a/2b, and Extension Visit 3)

This section summarizes prerequisites for vaccination visits in the extension study. See the inclusion/exclusion criteria for specific restrictions on Extension Visit 1 (see Section 5.1.2 and Section 5.2.2). At Extension Visit 2a/2b, and Extension Visit 3, study personnel should verify by questioning the participant and/or by examination that:

1. The participant has not had a fever (oral temperature ≥37.5°C) within the 24-hour period prior to the vaccination visit.

If the participant does not meet the requirements listed above, the study visit should be rescheduled.

8.12.3 Participants Discontinued From Study Intervention but Continuing to be Monitored in the Study

Participants who discontinue study vaccinations but continue in the study will attend study visits per the SoA including sampling of swabs, and/or biopsies specimens (Section 1.3) in the base study. However, serum will not be collected at the Month 7 study visit or subsequent visits from participants who did not complete the 3-dose study vaccination regimen.

V503-064-03 FINAL PROTOCOL 24-SEP-2024

9 KEY STATISTICAL CONSIDERATIONS

This section outlines the statistical analysis strategy and procedures for the study. If, after the study has begun, but prior to any unblinding/final database lock, changes are made to primary and/or secondary hypotheses, or the statistical methods related to those hypotheses, then the protocol will be amended (consistent with ICH Guideline E-9). Changes to exploratory or other non-confirmatory analyses made after the protocol has been finalized, but prior to unblinding/final database lock, will be documented in a supplemental statistical analysis plan (sSAP) and referenced in the CSR for the study. Post-hoc exploratory analyses will be clearly identified in the CSR.

9.1 Statistical Analysis Plan Summary

Key elements of the statistical analysis plan are summarized below; the comprehensive plan is provided in Sections 9.2 to 9.12. The same analysis plan for analysis populations and methods without hypothesis testing will be applied to evaluate decreasing of selected efficacy and immunogenicity endpoints from the first database lock for primary analysis, by using data up to the end-of-base-study (the database lock after the completion of the final efficacy sample assessment for the final efficacy analysis and after the last participant's Final Visit in the base study for the final immunogenicity and safety analysis). Descriptive analysis of selected safety endpoints will be reported in an end-of-base-study report and an extension study report.

Study Design Overview	A Phase 3, randomized, placebo-controlled clinical study to evaluate the efficacy, immunogenicity and safety of the 9vHPV vaccine in Japanese males, 16 to 26 years of age.
Treatment Assignment	All enrolled participants will be randomized in a 1:1 ratio to the 9vHPV vaccine group or placebo group.
Analysis Populations	Efficacy: Pre-Protocol Efficacy (PPE) population Immunogenicity: Per-Protocol Immunogenicity (PPI) population Safety: All Participants as Treated (APaT) population
Primary Endpoint	Efficacy: HPV 6/11/16/18-related anogenital persistent infection
Key Secondary Endpoints	 Efficacy: HPV 31/33/45/52/58-related anogenital persistent infection Immunogenicity: GMTs to each of HPV 6, 11, 16, 18, 31, 33, 45, 52, and 58 at 1 month post last dose (Month 7). Seroconversion to each of HPV 6, 11, 16, 18, 31, 33, 45, 52, and 58 at 1 month post last dose (Month 7).

08PSXL

Statistical Methods for Efficacy Analyses	The primary efficacy hypothesis will be evaluated by comparing the 9vHPV vaccine with placebo with respect to the primary efficacy endpoint. The p-value for testing the hypothesis that vaccine efficacy (VE) is greater than 0% as well as 95% confidence interval (CI) for VE will be provided using the exact binomial method proposed by Chan and Bohidar (1998) [Chan, I. S. F. and Bohidar, N. R. 1998]. The statistical criterion for success requires that the lower bound of the 2-sided 95% CI for VE against the primary efficacy endpoint is greater than 0%. The secondary efficacy hypothesis will be evaluated by comparing the 9vHPV vaccine with placebo with respect to the secondary efficacy endpoint based on the same method to be used in testing the primary efficacy hypothesis. The statistical criterion for success requires that the lower bound of the 2-sided 95% CI for VE against the secondary efficacy is greater than 0%.
Statistical Methods for Immunogenicity Analyses	The secondary immunogenicity objective will be addressed by summarizing antibody titer responses measured using cLIA at Month 7. The GMTs and the corresponding 95% CIs will be estimated based on the t-distribution for HPV types of 6, 11, 16, 18, 31, 33, 45, 52, and 58. Point estimates and the corresponding 95% CIs of percent seroconversion will be provided using the exact binomial method of Clopper and Pearson [Clopper, C. J. and Pearson, E. S. 1934] for HPV types of 6, 11, 16, 18, 31, 33, 45, 52, and 58, for all participants, HM group and MSM group, respectively.
Statistical Methods for Key Safety Analyses	There are no Tier 1 AEs identified in this study. For Tier-2 AEs, 95% CIs will be provided for between-treatment differences in the percentage of participants with events using the methods proposed by Miettinen and Nurminen [Miettinen, O. and Nurminen, M. 1985].
Interim Analyses	No interim analyses are planned in this study.
Multiplicity	The overall type 1 error rate associated with testing the primary and secondary efficacy hypotheses will be controlled to not exceed 0.025 (1-sided) by a fixed sequence procedure. The secondary efficacy hypothesis will be tested only if the primary efficacy hypothesis is successfully demonstrated.

Sample Size and Power

Testing the primary efficacy hypothesis with 17 total cases has 94% power to demonstrate that the efficacy of the 9vHPV vaccine compared to placebo is greater than 0% at 1-sided type 1 error rate \leq 0.025 if the underlying true VE against the primary efficacy endpoint is at least 85%.

Testing the secondary efficacy hypothesis with 17 total cases has also 94% power to demonstrate that the efficacy of the 9vHPV vaccine compared to placebo is greater than 0% at an overall 1-sided type 1 error rate \leq 0.025 if the underlying true VE against the secondary endpoint is at least 85%.

A total of approximately 1050 participants are needed to be enrolled in order to accumulate approximately 17 total primary endpoint cases and at least 17 total secondary efficacy endpoint cases within 56 months from the time the first study participant signs the ICF.

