9.8 Multiplicity

The overall type 1 error rate associated with testing the primary and secondary efficacy hypotheses will be controlled by a fixed sequence procedure. When at least 17 cases of the primary endpoint and at least 17 cases of the secondary endpoint have been observed, the primary efficacy hypothesis will be tested at a 1-sided type 1 error rate ≤ 0.025 , as discussed in Section 9.9.1. The secondary efficacy hypothesis will be tested at a 1-sided type 1 error rate ≤ 0.025 only if the primary efficacy hypothesis is successfully demonstrated.

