9.9.2 Sample Size and Power for Testing the Secondary Efficacy Hypothesis

Table 8 also displays the decision rule that will be used for testing the secondary efficacy hypothesis with 17 or more total cases. The testing of the secondary efficacy hypothesis of VE >0% at 17 total cases will have 1-sided type 1 error rate \leq 0.025 and power has 94% if the true VE is at least 85% (see Table 8).

A total of approximately 1050 participants are needed to be enrolled in order to accumulate at least 17 total secondary endpoint cases at the time of accumulation of at least 17 primary efficacy cases, i.e., within 56 months from the time the first study participant signs the ICF, when the annual incidence rate of the secondary efficacy endpoint is 2.0% per year and true VE is equal to 85% (based on the same enrollment duration, attrition, and exclusions from the PPE population assumed in Section 9.9.1.

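### The 94% power stated for the secondary efficacy hypothesis is for that test alone; through the fixed sequence it is 88% to 94% (17 cases each, VE 85% for both)

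*Combined protocol and SAP*

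**What the plan says.** The Sample Size and Power part of Section 9.1 gives 94% power for the primary hypothesis at 17 cases and then says of the secondary: "Testing the secondary efficacy hypothesis with 17 total cases has also 94% power to demonstrate that the efficacy of the 9vHPV vaccine compared to placebo" exceeds zero. The only efficacy condition attached is "if the underlying true VE against the secondary endpoint is at least 85" percent. Section 9.9.2 says the same: "The testing of the secondary efficacy hypothesis of VE >0% at 17 total cases will have 1-sided type 1 error rate" of at most 0.025 and power of 94% at VE 85%. It points to Table 8, which is titled for the primary hypothesis.

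The Multiplicity part of Section 9.1 says the overall error rate "will be controlled to not exceed 0.025 (1-sided) by a fixed sequence procedure", and continues: "The secondary efficacy hypothesis will be tested only if the primary efficacy hypothesis is successfully demonstrated". Section 9.8 repeats that the secondary is tested "only if the primary efficacy hypothesis is successfully demonstrated", and sets the analysis time as "When at least 17 cases of the primary endpoint and at least 17 cases of the secondary endpoint have been observed".

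No section gives the probability of demonstrating the secondary hypothesis under that sequence, and neither power statement says that 94% leaves the sequence out.

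**The concern.** Under the fixed sequence, a secondary case split that meets the Table 8 rule counts for nothing if the primary has failed. The probability of demonstrating the secondary hypothesis is therefore the probability that both tests succeed. It cannot exceed the power of either test and is lower unless the two succeed together every time.

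This matters because the secondary hypothesis covers types 31, 33, 45, 52 and 58, the five that this vaccine adds to the quadrivalent vaccine (Section 2.1). Someone planning around that claim will read 94% power to demonstrate efficacy as the chance of formally showing it. The design gives less in every case short of complete dependence, and the chance also depends on efficacy against the primary endpoint, which the secondary statements do not name as a condition.

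**Working it through.** **Inputs.** 1:1 randomization, at most 4 vaccine cases out of 17 for success, type 1 error 0.0245 and power 94% at VE 85% (Table 8, Section 9.9.1). Table 8 also governs the secondary test (Section 9.9.2). The test is the exact conditional binomial of Section 9.6.1. Annual incidence is 1.9% for the primary endpoint (Section 9.9.1); for the secondary, the plan gives "annual incidence rate of the secondary efficacy endpoint is 2.0% per year". The documents give no correlation between the endpoints.

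**Step 1: reproduce the plan's figure.** With equal person-years, the number of vaccine cases X is Binomial(17, π), where π = (1 − VE)/(2 − VE) = 0.15/1.15 = 0.1304.

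- Power: P(X ≤ 4 | 17, 0.1304) = 0.93947, the stated 94%.
- Type 1 error: P(X ≤ 4 | 17, 0.5) = 0.0245, as in Table 8.

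The Table 8 rows for 17 to 25 cases all reproduce in the same way.

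**Step 2: power through the sequence, 17 cases each, VE 85% for both.** Let p₁ and p₂ be the single-test powers of the primary and secondary tests.

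- Independent case splits: p₁ × p₂ = 0.93947² = 0.8826.
- Lower bound under any dependence: p₁ + p₂ − 1 = 2 × 0.93947 − 1 = 0.8789.
- Upper bound: min(p₁, p₂) = 0.9395.
- If k of the 17 cases are common to both endpoints, the two vaccine counts share a Binomial(k, π) part: k = 5 gives 0.8895, k = 8 gives 0.8955, k = 17 gives 0.9395.

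**Step 3: dependence on the primary VE (secondary VE 85%, 17 cases each).**

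- Primary VE 80%: p₁ = 0.86036. Independent: 0.86036 × 0.93947 = 0.808. Bounds: 0.86036 + 0.93947 − 1 = 0.800 to 0.860.
- Primary VE 90%: p₁ = 0.9849. Independent: 0.9849 × 0.93947 = 0.925.

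**Step 4: equal VE in other Table 8 columns (17 cases each, independent).**

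| True VE, both | Single test | Both tests |
|---|---|---|
| 75% | 0.7582 | 0.7582² = 0.575 |
| 80% | 0.8604 | 0.8604² = 0.740 |
| 85% | 0.9395 | 0.9395² = 0.883 |
| 90% | 0.9849 | 0.9849² = 0.970 |

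**Step 5: more than 17 secondary cases (17 primary, VE 85% for both, Table 8 rules, independent).** With the same VE, follow-up and exclusions, the plan's incidence rates imply 17 × 2.0/1.9 = 17.9 secondary cases when the primary reaches 17.

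| Secondary cases | Secondary test alone | Both tests |
|---|---|---|
| 18 | 0.9249 | 0.9395 × 0.9249 = 0.869 |
| 19 | 0.9085 | 0.9395 × 0.9085 = 0.854 |
| 20 | 0.9625 | 0.9395 × 0.9625 = 0.904 |
| 25 | 0.9885 | 0.9395 × 0.9885 = 0.929 |

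For 18 to 25 secondary cases, the lowest value is at 19 and the highest at 25.

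**The case against.** No stated figure is miscalculated. Reporting power per hypothesis is common, both sentences have the test itself as their subject, and Table 8 is visibly a single-test table. The sequence rule stands just before the power statements in the Section 9.1 summary, and the sentence above the secondary one assumes a primary VE of at least 85%. A statistician could combine the pieces. At the design assumptions the loss is at most about 6 points, and 88% is still respectable power. The larger shortfalls arise at VE values that the plan does not use for design. Some positive dependence is plausible, because both endpoints come from the same participants and swabs, so the independence figure may be slightly low.

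Most of this bears on how serious the point is, and it is why the point is modest. It does not supply the missing label or figure. The Section 9.1 sentence also ties the secondary 94% to an overall type 1 error rate, which invites reading it as power within the sequential procedure. Unknown dependence is no obstacle, since the bounds need no correlation.

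One limit does stand: 88% to 94% applies at exactly 17 cases of each endpoint. If both counts vary from 17 to 25 under Table 8's rules, the independent figure at VE 85% runs from about 0.9085² = 0.825 (19 and 19) to 0.9885² = 0.977 (25 and 25). The added text must therefore state the case counts.

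**Conclusion.** The concern holds. The 94% is right for the secondary test alone and is not the power that the fixed-sequence design delivers. With 17 cases of each endpoint, equal person-years and true VE 85% for both, the power to demonstrate the secondary hypothesis is 88.3% under independence, an assumption the documents neither support nor exclude, and 87.9% to 93.9% whatever the dependence. At those counts and that VE, 94% is the ceiling. At the plan's own expected 18 or so secondary cases with 17 primary, the independent figure is 86.9%. This is an omission in the stated power, not a flaw in the testing procedure.

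**What to change.** In Sections 9.1 and 9.9.2, label 94% as the power of the secondary test taken alone at 17 cases and VE 85%. Then add a sentence to this effect: under the fixed-sequence procedure, the power to demonstrate the secondary hypothesis is about 88%, assuming independent case splits, 17 cases of each endpoint and true VE 85% for both (88% to 94% under any dependence). State that the figure also depends on the primary VE, for example about 81% under independence if the primary VE is 80%.

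Joint values for the other Table 8 columns (about 57% at VE 75%, 74% at 80% and 97% at 90%, independent, 17 cases each) would be a useful but optional addition.

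The cost is about two sentences in each section and a less favourable stated figure. Type 1 error control, decision rule, case trigger and sample size stay as they are.
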